Approximately 150 patients will be enrolled in the study. Patients undergoing PCI at MGH and BWH will be screened by study staff for inclusion/exclusion criteria. Study staff will obtain approval to approach eligible patients by the inpatient treating physicians. On the day following PCI, prior to discharge, suitable patients will be consented and onboarded with study staff, with the technical help of Wellframe.

Procedure for obtaining informed consent

We will use Partners electronic resources identify and screen patients for the eligibility criteria listed above.

We will focus on patients undergoing PCIs in the cardiac catheterization lab on Blake 9, and who are then admitted to Ellison 10 or 11 (inpatient cardiac telemetry floors). We will screen for both elective PCIs and those for after an MI. We will create a database of potentially eligible subjects and obtain permission to approach them. We will only approach patients that have given permission to be approached. We will contact either the patient's nurse or other care team member so this person can ask permission of the patient before the research coordinator talks to the patient.

We will also send an email explaining the study to the subjects' outpatient cardiologist. We will mail to cardiologists who are not in the Partners network.

We will also use the attached study flyer to advertise the study to patients on inpatient floors and in the cath lab, with nurse manager approval for the respective floors.

Eligible patients will be approached by the study coordinator on the day of their discharge. The study coordinator will then review the consent form and study procedure and obtain written consent from the patient. Study coordinators will use an iPad to go over the consent form with the patient. The subject and the study coordinator will sign electronic copies of the consent form using Adobe Sign. Subjects will be sent a copy of the consent form via email using the Partners send secure system. Subjects with any cognitive disability that prevents them from consenting for themselves will also prevent them from using the Wellframe application. Therefore, subjects who cannot consent for themselves will be excluded from the study. We will make it clear that participation in the study is voluntary and the subject can choose to withdraw from the study at any time.

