The demographics (Age, Sex, Race/Ethnicity) of those screened for our study will be collected for recruitment analyses. Subjects who are not approached for participation will be reviewed for outcomes. For anyone who declines to participate in our study, we will not review their charts for outcomes.

It will not be possible to obtain consent from all of these patients as some of them will have already left the hospital. Not obtaining consent from these patients will not be a risk to the patients as no active intervention will be made and all information obtained from the records will be deidentified and stored in a secure database.

Patients who leave the hospital on the day of their procedure or before a coordinator can approach them will be recruited via flyer and then a phone call. Patients will be approached in the cath lab before or after their procedure and given a flyer. Coordinators will explain the study to the patient and that their eligibility will be confirmed after their procedure if it has not occurred yet. We will call these patients at

least a day after their procedure and conduct informed consent over the phone. Those who did not receive a flyer or do not want to be contacted will not be called.

Informed consent will take place over the phone and the subject will sign the consent form electronically using Adobe Sign. This study involves minimal risk. We cannot mail to patients or ask their physician to speak with them first, because patients must begin the study at maximum a few days after their procedure. Patients can also refuse the study when talking to the research coordinator. Patients can simply stop using the app whenever they want with no risk associated with stopping. We will attempt to contact patients twice using contact information provided in Epic.

If a patient agrees to participate over the phone, after signing the consent form, we will send instructions on how to download the app (a PDF version of the brochure) via email. Patients can then download and begin using the app.

We think it is feasible to recruit some patients remotely for the intervention arm, but for those that do not answer their phone or do not download the application, we do not believe it is necessary or possible to contact them solely to obtain consent to review their records for the non-intervention group.

Onboarding with Wellframe

STEP 1: Download Wellframe

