A Smartphone-based Application Post-myocardial Infarction to Manage Cardiovascular Disease Risk
NCT03416920
Version Date: 12/28/19
[name], [name]
Statistical Analysis Plan

A. Background and Rationale:

The period between inpatient hospitalization for symptomatic coronary artery disease (CAD) and post-discharge office consultation remains a vulnerable interval for adverse outcomes. We sought to develop and evaluate a tool to help guide, reassure and educate patients during this susceptible time.

We aimed to recruit and onboard 150 patients who have undergone percutaneous coronary intervention (PCI) with a novel mobile health platform developed specifically for this population. The mobile application (app) includes educational about specific procedures (PCI) and diagnoses (coronary artery disease, acute myocardial infarction) as well as lifestyle education programs (hypertension, hyperlipidemia, diabetes, weight loss, smoking cessation). The app also utilizes live health care coaches to interact with participants virtually to facilitate adherence to outpatient follow up, enrollment in cardiac rehabilitation and achieve individually targeted goals.

B. Hypothesis:

Our overall hypothesis is that engagement with our smartphone application post PCI will correlate with increased rates of enrollment in cardiac rehabilitation amongst study participants as compared to historical controls.

C. Endpoints:

- C.1. Primary:** 90-day cardiac rehabilitation enrollment rates
- C.2. Secondary:** 30-day cardiac outpatient follow up attendance

D. General Study Design and Plan

- D.1. Design:** Multi-site stratified single-arm prospective study

- D.2. Type of controls:** Historical

D.2.a. Control ascertainment: Query of Research Patient Data Registry (RPDR) database (a centralized clinical data registry that gathers clinical information from various Partners hospital systems with a query tool that provides users with detailed medical record information on identified patient populations that meet user-defined characteristics and criteria such as diagnoses, procedures, medications and/or laboratory results) for subjects aged 21-85 years old who underwent percutaneous coronary intervention from 01/01/2015 through 12/31/2017.

D.2.b. Control matching: Controls matched for Age, Sex (M/F), State (MA/non-MA), PCI Type (MI/Elective), DM2 (Y/N), Partners PCP (Y/N), Insurance Type (Commercial/Medicaid/Medicare/Other), Site (MGH/BWH)

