30-day hospitalization	Admission date to a Partners hospital within 30 calendar days of incident PCI.
90-day hospitalization	Admission date to a Partners hospital within 90 calendar days of incident PCI.
Cardiac reason for hospitalization	Admission for chief complaint of cardiac etiology (ie CAD, CHF, arrhythmia), admission requiring cardiac consultation or admission to a cardiology ward unit.
30-day ER visit	Presentation to Partners ER or Urgent Care within 30 calendar days of incident PCI without subsequent hospitalization.
90-day ER visit	Presentation to Partners ER or Urgent Care within 90 calendar days of incident PCI without subsequent hospitalization.

90-day Cardiac Rehabilitation	Attendance of cardiac rehabilitation intake session at a Partners facility within 90 calendar days of incident PCI.
30-day Cardiac Follow Up	Attendance of cardiac outpatient follow up appointment at a Partners facility (with MD or NP) within 30 calendar days of incident PCI
30-day repeat PCI	Repeat percutaneous intervention on same or new coronary lesion within 30 days of incident PCI.
90-day repeat PCI	Repeat percutaneous intervention on same or new coronary lesion within 90 days of incident PCI.
90-day Stroke	Chart diagnosis of or admission for new stroke within 90 calendar days of incident PCI as noted in Partners EHR.
90-day Nonfatal MI	Chart diagnosis of or admission for myocardial infarction (without subsequent death) within 90 calendar days of incident PCI as noted in Partners EHR.
90-day CV Death	Documentation of death within 90 calendar days of incident PCI noted in Partners EHR with cause specified as secondary to CAD, CHF, Arrhythmia or other clear cardiovascular reason.
90-day All Cause Death	Documentation of death within 90 calendar days of incident PCI noted in Partners EHR.
Conversion Rate	Number of patients enrolled in Wellframe out of number of total patients eligible for study.
Days Enrolled	Number of days between patient onboarded with Wellframe app and marked done by clinical staff.
Medication Reminders	Number of medication reminders set up by patient (0 if patient has not set up any reminders).
30-day Medication Adherence	Percentage of medication reminder tasks completed within 30 days on app. (Null if no patient reminders set up)
90-day Medication Adherence	Percentage of medication reminder tasks completed within 90 days on app. (Null if no patient reminders set up)

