D.8. Sample size and power: We have at least 95 percent power with 150 enrolled participants, 450 matched historical controls, with alpha equal to 0.05, to detect an effect of at least 2-fold increase in the primary clinical outcome, likelihood of enrollment in cardiac rehabilitation within the 90 day study period with baseline 25% enrollment rates⁶.

E. General Considerations:

E.1. Analysis populations:

E.1.a.: Full analysis population: All intervention subjects who downloaded the study application and 3:1 matched historical controls.

E.1.b.: Engagement population: All intervention subjects who downloaded the study application.

E.2. Covariates and subgroups: Sex (M/F), State (MA/non-MA), PCI Type (MI/Elective), DM2 (Y/N), Partners PCP (Y/N), Insurance Type (Commercial/Medicaid/Medicare/Other)

E.3. Missing data: Missing data values for participants who fit inclusion criteria will default to zero or “no” for dichotomous variables. Missing data values for participants will default to “unknown” or “other” for continuous or categorical variables.

F. Summary of study data: All continuous variables will be summarized using the following descriptive statistics: n (non-missing sample size), mean, standard deviation, median, maximum and minimum. The frequency and percentages (based on the non-missing sample size) of observed levels will be reported for all categorical measures. In general, all data will be listed, sorted by site, treatment and subject, and when appropriate by visit number within subject. All summary tables will be structured with a column for each treatment in the order (Control, Experimental) and will be annotated with the total population size relevant to that table/treatment, including any missing observations.

G. Protocol deviations: Subjects who do not fit inclusion criteria will be removed from the data set prior to analysis. Subjects with missing data will be treated as discussed above (Section E.3.)

H. Efficacy Analyses: The Cox Proportional Hazards model will be used to assess efficacy of the intervention (use of the application) on the primary outcome. The percentage of subjects attending cardiac rehabilitation enrollment within 90 days of discharge from incident PCI hospitalization will be compared across groups. A secondary analysis between the two groups will be conducted adjusting for covariates such as age, sex, insurance type, state, diabetes, and partners PCP).

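### Deaths between PCI and app download can be counted only in controls, which biases the exploratory death comparisons toward the app; SAP D.7, H and J also use three different time origins

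*SAP*

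**What the plan says.** **Entry of app patients.** SAP E.1.a defines the full analysis population as "All intervention subjects who downloaded the study application and 3:1 matched historical controls". The protocol gives several times for reaching that point. The enrollment overview says "On the day following PCI, prior to discharge, suitable patients will be consented and onboarded with study staff". The consent procedure says "Eligible patients will be approached by the study coordinator on the day of their discharge". Patients who leave before a coordinator can see them are phoned at "least a day after their procedure and conduct informed consent over the phone" and then download the app themselves. The protocol adds that "patients must begin the study at maximum a few days after their procedure".

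**Entry of controls.** SAP D.2.a queries the registry "for subjects aged 21-85 years old who underwent percutaneous coronary intervention from 01/01/2015 through 12/31/2017". Neither that query, nor the eight matching factors in D.2.b, nor the eligibility criteria in D.6 requires a control to have been discharged alive or to have survived to any given day.

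**Clock.** SAP D.7 defines 90-day all-cause death as "Documentation of death within 90 calendar days of incident PCI noted in Partners EHR", and dates CV death, stroke, nonfatal MI and repeat PCI from the incident PCI as well. Section H counts the primary rehabilitation outcome from discharge, although D.7 counts it from PCI. Section J counts repeat PCI, stroke, MI and death over 90 days from enrollment. No enrollment date is defined for controls.

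**Status.** Section K makes everything except 90-day rehabilitation enrollment exploratory. Section J nevertheless describes the death models as assessing the efficacy of the intervention.

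**The concern.** Between PCI and download an app patient is immortal by construction, because someone who dies in that interval never enters the analysis set. A control who dies in the same interval stays in and is counted. With an identical true risk in both groups, the death rate would still come out lower with the app. Matching and covariate adjustment cannot remove this, because none of the variables involved carries survival to onboarding.

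The same gap touches the nonfatal outcomes, in both directions. An early disabling event, such as a stroke, makes onboarding unlikely, which favours the app. An early event that does not prevent onboarding, such as a repeat PCI in the same stay, is charged to the app before the patient had it.

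What is at stake is how the Section J models for CV and all-cause death, and the MACE table, would be read. An apparent reduction in deaths could arise wholly from how the two groups were assembled.

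**Working it through.** The plan states no expected death rate and no power for death, so there is no plan figure to reproduce on this point. Its one power statement (SAP D.8) concerns rehabilitation. It is met: 150 versus 450, 50% versus 25%, two-sided alpha 0.05 gives power above 99.9%, against the stated minimum of 95%. It does not bear on what follows.

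**Step 1: who can contribute a death.**

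| Interval | App patient | Control |
|---|---|---|
| PCI to download, or the matched day | cannot be counted | counted |
| After download, to day 90 | counted | counted |

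The direction for death follows from the definitions alone.

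**Step 2: inputs.**
- From the documents: 150 app patients, of whom 100 MI and 50 without MI (Protocol III, sample size); 3:1 matching, with PCI type a matching factor (SAP E.1.a, D.2.b), hence 300 MI and 150 elective controls.
- Assumed, because the documents give no figure: mortality after the landmark m = 2% in everyone; early mortality e = 1%, 3% or 5% in MI controls and 0 in elective controls; no true app effect.

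**Step 3: formulas.**
- Expected app deaths = 150 × m = 150 × 0.02 = 3.0, a risk of 2.00%.
- Risk in MI controls = e + (1 − e) × m.
- Expected control deaths = 300 × [e + (1 − e) × 0.02] + 150 × 0.02.

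**Step 4: results.**

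| e in MI controls | MI control risk | Control deaths | Control risk | Apparent risk ratio |
|---|---|---|---|---|
| 0% | 2.00% | 6.00 + 3 = 9.00 | 2.00% | 1.00 |
| 0.5% | 2.49% | 7.47 + 3 = 10.47 | 2.33% | 0.86 |
| 1% | 2.98% | 8.94 + 3 = 11.94 | 2.65% | 0.75 |
| 3% | 4.94% | 14.82 + 3 = 17.82 | 3.96% | 0.51 |
| 5% | 6.90% | 20.70 + 3 = 23.70 | 5.27% | 0.38 |

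The 0% row is also what a common landmark gives. The 0.5% row stands for a short window, such as onboarding the day after PCI.

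**Step 5: chance of a false finding.** With a control risk of 3.96% and an app risk of 2%, a two-sided Fisher test at 0.05 on 150 versus 450 shows a significant app benefit about 13% of the time, against 1.0% when there are no early deaths. This ignores matching and stands in for the Cox model.

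**Step 6: primary outcome.** Suppose early control deaths stay in the denominator as non-attenders. The 25% baseline rate of D.8 becomes 25% × (1 − 300e/450), which is 24.8%, 24.5% or 24.2% for e = 1%, 3% or 5%. The spurious ratio is at most 25/24.2 = 1.03.

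**The case against.** Several counter-arguments have force.

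- **The window may be about one day.** The overview has patients onboarded the day after PCI, before discharge. A reader might infer that all in-hospital deaths fall on controls only. The documents do not support that: an app patient can download on day 1, die later in the same stay and be counted. The condition is survival to download, so charging full in-hospital mortality to controls can overstate the bias. This stands.
- **A reader might extend the bias to the primary outcome.** Section H counts rehabilitation from discharge, and its table shell takes discharged patients as the denominator, which already removes in-hospital deaths. If the Cox model censors at death (the SAP states no rule), early deaths leave the risk set and do not count as non-attenders. Even the worst case in step 6 is trivial. This stands.
- **A reader might apply one direction to every outcome.** Pre-download nonfatal events are counted in both groups, and a control who dies early cannot later have a repeat PCI. The net direction for stroke, MI and repeat PCI cannot be established from the documents. This stands.
- **Larger ratios can be quoted.** In the MI patients alone (100 versus 300), the same assumptions give 2.00/2.98, 2.00/4.94 and 2.00/6.90, or 0.67, 0.40 and 0.29. The planned set is all app patients and their controls, so the 150 versus 450 figures are the relevant ones. With three expected app deaths, any estimate is imprecise.
- **Section J starts at enrollment.** That would help only if controls had an enrollment date. They have none, and D.7 still defines both death variables from PCI. This does not answer the point.
- **Death is exploratory.** Section K deals with multiplicity and does nothing about a bias that runs one way.

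**Conclusion.** The point holds for 90-day CV death, all-cause death and any death component of MACE (the SAP lists MACE without defining it). Deaths between PCI and download can be counted only in controls, and the bias favours the app. The direction is certain; the size is not. With 2% later mortality, no true effect and early mortality of 1% to 5% confined to MI controls, the apparent risk ratio runs from about 0.75 to 0.38. At 0.5% it is 0.86, and it approaches 1 as the window shortens.

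For stroke, nonfatal MI and repeat PCI there is misattribution without a known net direction. The primary conclusion on rehabilitation is not threatened. Separately, the time origins in D.7 (PCI), H (discharge) and J (enrollment) conflict and need reconciling. The change is worth making because it is cheap and the affected models are described as efficacy analyses.

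**What to change.** 1. Write one time origin into SAP D.7, H and J. For app patients it is the app download date. For each control it is the control's PCI date plus the matched app patient's PCI-to-download delay.
2. Apply the survival condition before 3:1 matching: for each app patient, only candidates alive at that landmark may be selected. Dropping controls after matching would break the 3:1 ratio.
3. If discharge alive is to be required, require it in both groups and start both at the later of discharge and the landmark in item 1. Requiring it of controls alone could reverse the bias, because app patients onboarded before discharge would remain at risk of in-hospital death.
4. In the Section J models for death, MACE, stroke, nonfatal MI and repeat PCI, count only events after the landmark.
5. Keep the PCI-dated analysis as a sensitivity analysis.

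Cost: SAP wording, dates of death and discharge from the RPDR query, a slightly smaller control pool, and possibly a less favourable app effect on death. The onboarding date is already needed for the Days Enrolled variable in D.7.

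One limit remains. A landmark secures that controls are alive, not that they were well enough to be onboarded. Controls disabled by an early event stay in, and the report should say so.
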